13.6 Monitoring

Safety Monitoring:

This study will be monitored by the Alliance Data and Safety Monitoring Board (DSMB), an NCI-approved functioning body. Reports containing efficacy, adverse event, and administrative information will be provided to the DSMB every six months as per NCI guidelines. In addition, the Study Chair and Study Statistician will review the accrual and safety data periodically, as well as the Alliance Group Meeting Reports, in order to identify any feasibility problems associated with accrual rates and adverse events.

Any data release, whether at the time of interim analysis or at the time of final analysis, must be approved by the Alliance DSMB prior to execution.

CDUS Monitoring: This study has been assigned CDUS Abbreviated monitoring.

This study will be monitored by the Clinical Data Update System (CDUS) Version 3.0. Cumulative protocol- and patient-specific CDUS data will be submitted electronically to CTEP on a quarterly basis by FTP burst of data. Reports are due January 31, April 30, July 31, and October 31. Instructions for submitting data using the CDUS can be found on the CTEP Web site

Note: If your study has been assigned to CDUS-Complete reporting, all adverse events (both routine and expedited) that have occurred on the study and meet the mandatory CDUS reporting guidelines must be reported via the monitoring method identified above. If your study has been assigned to CDUS-Abbreviated reporting, no adverse event reporting (routine or expedited) is required to be reported via CDUS, but expedited adverse events are still required to be submitted via CTEP-AERS.

Enhanced Centralized Data Monitoring: This trial will utilize central monitoring in order to ensure complete and consistent data collection.

Enhanced centralized data monitoring will be performed for the first two cycles of treatment for all patient cases enrolled from each site (as identified by a unique NCI Institution Code). The cases selected for central monitoring will be reviewed for completeness and consistency with the eligibility criteria via source data verification (SDV) with source documents compared to data reported via the electronic Case Report Forms in Rave. Centralized data monitoring with SDV will be performed for all patients for key eligibility and response/disease outcomes.

A source document is a document in which data collected for a clinical trial is first recorded. This data is usually later entered in the Case Report Forms. The ICH-GCP guidelines define source documents as original documents, data, and records.

The pretreatment documents that should be uploaded within two weeks after registration for central review include:

- 1) Pathology report
- 2) Baseline imaging reports used to confirm radiographic progression for eligibility
- 3) Documentation of one or more prior lines of FDA-approved systemic therapy (as specified in Section 3.2.3) not including somatostatin analogs and documentation of disease progression or treatment intolerance
- 4) Labs to include baseline CBC, chemistry, urine protein to creatinine (UPC) ratio, TSH
- 5) ECG
- 6) Clinic source documents to verify initial performance status
- 7) Deidentified last page of the signed and dated informed consent document including any pages with responses indicated by patient for optional studies (with patient's full signature and any other PHI redacted, but date should be retained)
- 8) Documentation of the first two courses of treatment (submitted within two weeks of completion) to include, medication orders, medication compliance records

See the Data Submission Schedule, available on the Alliance and CTSU websites, for additional details regarding source data verification of key eligibility criteria.

Sites should ensure that patient identifiers have been removed from all pages that will be uploaded and add study-specific identifying information (i.e. Alliance Patient ID) and then scan and upload all document into Rave. Please ensure that all pages are legible and correct.

In the event that enhanced central monitoring or review of key performance indicators (KPIs) identifies unacceptable enrollment procedures or significant deviations from eligibility criteria, treatment administration, or other significant protocol requirements, then the site will need to submit a corrective and preventative action plan (CAPA) within two weeks of being notified of the findings of the central monitoring.

Additional cases may be selected for centralized monitoring or an audit visit may be conducted when deviations are noted or for sites will high enrollment (note: audit visits will be conducted according to the NCI Clinical Trials Monitoring Branch guidelines). Deficiencies or KPIs that may elicit one of these responses include, but are not limited to:

- Accrual rate
- Eligibility
- Early termination
- Data submission timeliness
- Outstanding forms
- Outstanding queries
- Query responsiveness
- Protocol deviations

13.7 Descriptive Factors

Tumor Grade: grade 1 vs. grade 2 vs. grade 3 vs. unknown

Functional (Hormone Secretion) Status: functional vs. non-functional

Tumor Site: pancreatic vs. lung vs. stomach vs. duodenum vs. jejunum vs. ileum vs. appendix vs. cecum vs. ascending colon vs. hepatic flexure vs. transverse colon vs. splenic flexure vs. descending colon vs. sigmoid colon vs. rectum vs. unknown vs. other

13.8 Inclusion of Women and Minorities

Pancreatic NET Cohort

	DOMESTI	C PLANNED E	NROLLMENT R	EPORT	
		Ethnic (Categories		
Racial Categories	Not Hispan	ic or Latino	Hispanic	or Latino	Total
	Female	Male	Female	Male	
American Indian/ Alaska Native	2	2	0	0	4
Asian	6	7	0	0	13
Native Hawaiian or Other Pacific Islander	8	10	0	0	18
Black or African American	3	3	1	1	8
White	63	66	5	4	138
More Than One Race	2	2	0	0	4
Total	84	90	6	5	185

Carcinoid Tumor Cohort

	DOMESTI	C PLANNED EN	ROLLMENT RI	EPORT	
		Ethnic C	ategories		
Racial Categories	Not Hispan	ic or Latino	Hispanic	or Latino	Total
	Female	Male	Female	Male	
American Indian/ Alaska Native	3	3	1	1	8
Asian	6	7	0	0	13
Native Hawaiian or Other Pacific Islander	8	10	0	0	18
Black or African American	4	4	2	2	12
White	69	73	6	5	153
More Than One Race	2	2	1	1	6
Total	92	99	10	9	210

14.0 CORRELATIVE AND COMPANION STUDIES

There will be one substudy and one biobanking for future correlative science studies, and all patients are encouraged to participate.

14.1 Quality of Life Substudy (Alliance A021602-HO1)

14.1.1 Background

We will evaluate quality of life and disease-related symptoms in patients with advanced pancreatic NET and carcinoid tumors treated with cabozantinib versus placebo. For patients who opt in, patients will complete the EORTC QLQ-C30 and EORTC QLQ-GI.NET21 at baseline and every 12 weeks until disease progression or the start of a new anticancer therapy. The hypothesis is that cabozantinib will improve quality of life and decrease disease-related symptoms as compared to placebo and will be important in the current study to investigate potential treatment benefits in the setting where no effective treatments exist. We are using the same tools as were used in A021202 (randomized phase II study of pazopanib versus placebo in patients with progressive carcinoid tumors) to allow for cross-study comparison and to further our current work in understanding quality of life and disease symptomatology of these patients. In A021202, the EORTC QLQ-C30, GI.NET21, and Linear Analog Self-Assessment (LASA) items were administered at baseline, weekly during the first cycle of treatment, at 3 months, and at 1 year with a plan to compare the longer questionnaires (EORTC QLQ-C30 and GI.NET21) to a brief approach (LASA items). We have modified our approach somewhat in the present study maintaining the longer questionnaires (as results indicating comparability of approaches is not available at this time) but capturing less acute data and more frequent long-term data on the same schedule as disease assessments to better estimate and compare the trajectory of disease impact over time as well as to begin to explore possible symptom response endpoints for use in future clinical trials. Note, patient-reported treatment-related toxicities will be captured in the main body of the protocol using PRO-CTCAE on a more frequent interval.

Recently, Pearman et al. [40] reported a large cross-sectional study using the PROMIS-29 questionnaire reported on the quality of life outcomes of patients with NET. The authors report that increased frequency of bowel movements and presence of flushing symptoms

are correlated with decreased quality of life. Also, patients with recurrent disease reported poorer physical, social, and mental functions. This study was consistent with a previous study reported by Beaumont et al. [41].

A major limitation of these studies was their cross-sectional approaches in heterogeneous patient populations. Investigation of quality of life in this patient population in the setting of therapeutic clinical trials remains lacking. The present study allows us to estimate the within-patient trajectory of disease impact over time and compare trajectories between arms in a well-defined clinical trial population. We also aim to explore possible symptom response endpoints to begin to develop criteria for evaluating future therapies in clinical trials in this patient population.

14.1.2 Methods

For the schedule of assessments for this quality of life study, see Section 5.0. All participating institutions must ask patients for their consent to participate in this quality of life study (A021602-HO1), although patient participation is optional. Paper booklets will be used for this study. For information regarding ordering the booklets, see Section 4.3. For all patients who consent to participate in the quality of life study (A021602-HO1), a booklet will be given to the patient to complete at the specified, planned clinic visits before any procedures/tests are initiated at the site visit and prior to any discussion of their status with healthcare personnel at the site. For assessments after cessation of protocol-treatment but prior to disease progression or the start of a new anticancer therapy, a member of the site study staff may administer the booklet over the phone if no clinic visit is available for in-person completion. Booklets will be collected at the following time points: at baseline and every 12 weeks until disease progression or initiation of new anticancer therapy (i.e. every 3 cycles approximately coinciding with disease assessments). The booklet contains 52 questions, and it is anticipated that the booklet will take approximately 10-15 minutes for the patient to complete at each administration time point. The questionnaires will be available in pre-printed booklets in English at time of study activation. Booklets containing other languages may be added depending on patient demand. Patients who consent to participate in this quality of life study (A021602-HO1) may decline to complete a booklet at any time. The primary reason for each missed booklet will be collected on a case report form.

The European Organisation for Research and Treatment of Cancer Quality of Life Questionnaire Core 30 (EORTC QLQ-C30) is a 30-item questionnaire about patient ability to function (measured via five functional scales), symptoms related to the cancer and its treatment (via eight symptom scales/items), overall health and quality of life, and perceived financial impact of the cancer and its treatment. Each item is measured on a 1-4 scale (1=not at all; 4=very much). Seven of nine scales had Cronbach's alpha greater than 0.70 and the test-retest reliability for all scales and one single item was 0.78 or higher. These instruments are available in other languages upon request.

The GI.NET21 module is intended for use among patients with gastrointestinal-related neuroendocrine tumors, who vary in disease stage and treatments. The module comprises 21 questions assessing disease symptoms, side effects of treatment, body image, disease-related worries, social functioning, communication and sexuality. The questionnaire results in the following scale scores: endocrine symptoms [3 questions], gastrointestinal symptoms [5 questions], treatment-related side effects [3 questions], bone/muscle pain [1 question], concern about weight loss [1 question], social function [3 questions], disease-related worries [3 questions], sexuality [1 question], and communication [1 question]. The measure is presently in phase IV validation testing as set out in the EORTC module

development process, indicative that initial content and construct validity has been achieved, but that further data are needed to demonstrate responsiveness and discriminant validity. Given the lack of an alternative fully validated NET-specific questionnaire, and the EORTC's rigorous development process and high rate of ultimately successful validation, we have selected to use this questionnaire for the current study. We believe that this questionnaire will become the gold standard for assessment of quality of life issues in patients with NET.

Perception of change will be evaluated with a Patient Global Impression of Change item. Global Impression of Change Scale (also called the Subjective Significance Scale) has been used as an anchor for determination of minimally clinically significant differences in numerous oncology clinical trials within Alliance legacy trials (N00C3, N01C3, N01CB, and N03CA) and beyond [42-44]. The patient rates the change in his/her overall status (ranging from very much improved, much improved, minimally improved, no change, minimally worse, much worse, to very much worse).

14.1.3 Objectives/Hypotheses

Primary Objective

Compare health-related quality of life (HRQL) as assessed by the EORTC QLQ-C30 between patients randomized to cabozantinib vs. placebo by patient cohort (pancreatic NET vs. carcinoid tumor).

Hypothesis: HRQL (based on the EORTC QLQ-C30 HRQL summary score) will be better in patients randomized to cabozantinib compared to placebo from initiation of protocol-treatment until disease progression or start of new anticancer therapy.

Secondary Objective

Compare NET disease-related symptoms and other domains as assessed by EORTC QLQ-GI.NET21 between patients randomized to cabozantinib vs. placebo by patient cohort (pancreatic NET vs. carcinoid tumor).

Hypothesis: NET disease-related symptoms and other domains (based on the EORTC QLQ-GI.NET21 scale scores excluding treatment-related side effects and communication) will be better in patients randomized to cabozantinib compared to placebo from initiation of protocol-treatment until disease progression or start of new anticancer therapy.

Exploratory Objectives

- 1) Assess the relationship between EORTC QLQ-GI.NET21 symptoms, EORTC QLQ-C30 functioning domains, and EORTC QLQ-C30 Global Health Status/Quality of Life score.
- 2) Explore possible symptom response definitions through estimation of meaningful changes in EORTC QLQ-GI.NET21 scale and summary scores and compare rates of symptom response between arms.

14.1.4 Statistical Considerations

All questionnaires will be scored according to published scoring algorithms. The primary analysis will involve a mixed model of the EORTC QLQ-C30 HRQL summary score within each patient cohort. The mixed model will compare the post-randomization HRQL between randomized arms. In addition to a randomized arm covariate, each model will include a covariate for baseline HRQL and will use the planned month of assessment as the categorical time value. Unstructured covariance will initially be used, though alternative covariance structures will be investigated with the final covariance structure

selected based on minimization of the Akaike information criterion. The statistical significance of the randomized arm covariate between arms will be employed for hypothesis testing. Within this model, this covariate represents the estimated average difference between randomized arms across post-randomization time points. We have chosen this approach to reduce the number of hypothesis tests to one for each patient cohort. We feel that this is a reasonable approach because we anticipate a consistent effect across time points. In supplemental analysis, we will modify this approach to include a time-by-arm interaction effect and report time-specific comparisons between arms as well as model-based estimation of the area-under-the-curve throughout treatment based on mixed model contrasts.

Primary patient-reported outcome analysis will be conducted at the time that all consented patients have completed 24 weeks of treatment (or are no longer being followed for quality of life). Release of the data for presentation will be at the discretion of the DSMB. Patients will be analyzed according to the randomized treatment arm assignment. All patients who consent for participation in the HO1 component with a baseline endpoint value and at least one endpoint value post-randomization will be included in the primary analysis. In the primary analysis, all observations available will be used. See below for information regarding analyses to account for missing data.

In secondary analysis, similar mixed model comparisons of EORTC QLQ-GI.NET21 scale scores will be conducted within each patient cohort. Graphical procedures will include plots of average values over time by arm for each primary and secondary endpoint. Exploratory analysis will include computation of Pearson correlations among patient-reported endpoints at fixed time points and univariate and multivariate linear mixed models of EORTC QLQ-C30 Global Health Status/Quality of Life score to investigate the impact of symptoms and functioning on quality of life.

Possible symptom response endpoints will be explored. Candidate summary scores include the average of all EORTC QLQ-GI.NET21 scale scores and the average of all EORTC QLQ-GI.NET21 scale scores excluding treatment-related side effects and communication. Meaningful change for each will be explored using common distribution-based and anchorbased approaches. Data will be pooled across patient cohorts for this analysis. For distribution-based approaches, meaningful changes will be estimated as 0.5 and 0.3 times the baseline standard deviation, 12-week standard deviation, 24-week standard deviation, standard deviation of the change-from-baseline scores at 12 weeks, and standard deviation of the change-from-baseline scores at 24 weeks. The anchor-based approach will employ the global impression of change items at 12 and 24 weeks. Candidate symptom response endpoints with triangulated meaningful change criteria will be applied to each treatment arm and rates of symptom response will be compared between arms within each patient cohort using a chi-squared test. Finally, cumulative distribution plots will be used to visually simultaneously assess arm comparisons across all possible meaningful change criteria within each patient cohort.

For all statistical analyses, p-values <0.05 will be considered statistically significant (though interpretation will take into consideration that the type I error is not strictly controlled across primary and secondary endpoints). For interpreting the clinical significance of effects, 0.2, 0.5, and 0.8 standard deviation (SD) effects will be considered as small, moderate, and large based on Cohen throughout [45].

Missing data will be handled in a number of ways. Missing items within a summary or scale score will be handled according to each questionnaire's published scoring algorithms. Missing data at the summary or scale score level will be handled as follows. Baseline

patient/disease characteristics will be compared between patients who do and do not provide data for the primary analysis. We will also graphically explore patterns of missing data. All analyses will be completed using all available data, followed by analyses completed using a range of imputation methods. Lastly, we will employ pattern mixture models for longitudinal analyses. Output from all analyses will be tabulated and descriptively compared to assess the degree to which missing data impacts study results.

Power

Within the **pancreatic NET cohort**, we assume that 138 of the 185 enrolled patients will be progression-free at 12 weeks (based on median PFS of 5 months in the placebo arm and 8.8 months in the cabozantinib arm). Allowing up to 15% additional missing data due to non-compliance, we based power estimation on having baseline and at least one follow-up assessment in 117 patients (83 on the cabozantinib arm, 34 on the placebo arm) in this cohort. The primary analysis in this cohort has 80% and 90% power to detect a 0.58 and a 0.67 standard deviation difference between arms, respectively, assuming no correlation between baseline and follow-up HRQL (conservatively based on a power calculation for a two-sample t-test). With correlation of 0.5 between baseline and a single follow-up HRQL, the detectable effect size shrinks to 0.52 and 0.61, respectively, which can still be thought of as a conservative estimate based on a single follow-up time point.

Within the **carcinoid tumor cohort**, we assume that 169 of the 210 enrolled patients will be progression-free at 12 weeks (based on median PFS of 7 months in the placebo arm and 12 months in the cabozantinib arm). Allowing up to 15% additional missing data due to non-compliance, we based power estimation on having baseline and at least one follow-up assessment in 143 patients (100 on the cabozantinib arm, 43 on the placebo arm) in this cohort. The primary analysis in this cohort has 80% and 90% power to detect a 0.51 and a 0.60 standard deviation difference between arms, respectively, assuming no correlation between baseline and follow-up HRQL (conservatively based on a power calculation for a two-sample t-test). With correlation of 0.5 between baseline and a single follow-up HRQL, the detectable effect size shrinks to 0.47 and 0.55, respectively, which can still be thought of as a conservative estimate based on a single follow-up time point.

The planned analyses will incorporate all available data to maximize power. Thus, we anticipate having 80% power for detecting an effect size between 0.4 and 0.5 standard deviations within each cohort which is considered as clinically meaningful based on the work of Cohen.

Overall power across both cohorts is expected to be 81% (i.e. $0.90 \times 0.90 = 0.81$) for effect sizes of 0.67 and 0.60 in the pancreatic NET and carcinoid tumor cohorts, respectively, assuming no correlation between baseline and follow-up HRQL, and for effect sizes of 0.61 and 0.55 in the pancreatic NET and carcinoid tumor cohorts, respectively, assuming a correlation of 0.5 between baseline and follow-up HRQL. These effect sizes are considered moderate to large and clinically-meaningful based on the work of Cohen.

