4.6 Stratification and Grouping Factors and Treatment Assignments

Grouping Factors: Pancreatic NET vs. Carcinoid Tumor (i.e. non-pancreatic NET)

Randomization will be done separately within each cohort, pancreatic NET vs. carcinoid tumor.

Permuted Block

After a patient is registered, they will be assigned to one of the two treatment arms (cabozantinib vs. placebo) in a **2:1** ratio utilizing a permuted block schedule [37]. The goal of the algorithm is to maintain arm balance with respect to the following important stratification factors:

Stratification Factors for the Pancreatic NET Cohort:

- Concurrent Somatostatin Analog Use: Yes vs. No
- Prior Sunitinib Therapy: Yes vs. No

Stratification Factors for the Carcinoid Tumor Cohort:

- Concurrent Somatostatin Analog Use: Yes vs. No
- Primary Site: Midgut (jejunum, ileum, appendix, cecum, ascending, colon, hepatic flexure)/Unknown primary site vs. Non-midgut GI (stomach, duodenum, transverse colon, splenic flexure, descending colon, sigmoid colon, rectum)/Lung/Other known primary site not listed

When combined, these stratification factors create four stratum levels for each cohort, and each stratum level will have its own patient allocation schedule. The possible block size for this study is six.

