13.0 STATISTICAL CONSIDERATIONS

This study is a two-arm randomized, double-blinded, placebo-controlled phase III trial comparing the outcomes of treatment with 1) cabozantinib or 2) placebo in patients with advanced neuroendocrine tumors after progression on prior therapy. Patients will be separated into 2 cohorts: pancreatic NET vs. carcinoid tumors. Patients will be randomized in 2:1 fashion to either cabozantinib or placebo. The randomization will be done separately within each cohort. Efficacy analyses will be based on the intention to treat principle, and all randomized patients will be included for the analysis, i.e. patients will be assigned to the treatment group they were randomized to regardless of the actual treatment received. Analysis related to adverse events will be based on the safety population. All patients who were randomized and received any amount of protocol therapy will be considered in the safety population, and patients will be assigned to the treatment group they actually received.

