13.4 Stratification

The analysis will be done separately for the pancreatic NET and carcinoid tumor cohorts and will be stratified by the stratification factors listed in Section 4.6.

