Analysis plan for both cohorts: PFS will be compared between treatment arms using the stratified log rank test at one-sided level 0.023. The stratification factors listed in Section 4.6, as collected on the OPEN Enrollment Form, will be used for the analysis. The HR for PFS will be estimated using a stratified Cox proportional hazards model, and the 95% CI for the HR will be provided. Results from an unstratified analysis will also be provided. Kaplan-Meier methodology will be used to estimate the median PFS for each treatment arm, and Kaplan-Meier curves will be produced. Brookmeyer Crowley methodology will be used to construct the 95% CI for the median PFS for each treatment arm [39].

Sensitivity analysis plan for both cohorts:

- The PFS according to investigator assessment will be used as the endpoint for a sensitivity analysis.
- For patients with a PFS event related to the results of a scan performed prior to the time of scheduled restaging, the PFS event will be dated on the date of the next scheduled radiology restaging assessment.

Carcinoid Tumor Cohort – Pre-planned Subgroup Analysis

In the carcinoid tumor cohort, we will perform the subgroup analysis by the subgroups specific below to evaluate whether the treatment effect is consistent across different subgroups. Interaction p-value (interaction between treatment arms and specific subgroups) will be used to determine whether the treatment effect is consistent. A p-value of < 0.1 will indicate that there is a differential treatment effect across different subgroups.

The pre-planned subgroups are:

- Prior Anti-VEGF Therapy: Yes vs. No
- Prior Targeted Radionucleotide Therapy (PRRT): Yes vs. No

[‡] Proportions are based on 10,000 replicates in the simulation study.

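### The quality-of-life mixed models do not name the randomisation stratification factors, and Section 13.4 does not clearly supply them: a small efficiency and specification point

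*Combined protocol and SAP*

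**What the plan says.** Section 4.6 randomises separately within each cohort, by permuted blocks, on two binary factors per cohort. Both cohorts use concurrent somatostatin analog use. The second factor is prior sunitinib in pancreatic NET and primary-site group in carcinoid. The section explains that "The goal of the algorithm is to maintain arm balance with respect to the following important stratification factors", that "these stratification factors create four stratum levels for each cohort, and each stratum level will have its own patient allocation schedule", and that "The possible block size for this study is six". Section 13.0 gives the 2:1 allocation.

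Section 14.1.4 describes the primary quality-of-life analysis: a mixed model of the QLQ-C30 summary score, fitted within each cohort. Besides the arm term, "each model will include a covariate for baseline HRQL and will use the planned month of assessment" as a categorical time variable. The secondary GI.NET21 scales get similar models. The stratification factors are not mentioned for either.

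Section 13.4 says that the analysis is done by cohort and "will be stratified by the stratification factors listed in" Section 4.6. Section 13.5.1 applies this to PFS: "The stratification factors listed in Section 4.6, as collected on the OPEN Enrollment Form, will be used for the analysis". Section 13.5.2 uses a stratified log-rank test and stratified Cox regression for OS. Section 14.1.4 does not refer to Section 13.4.

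**The concern.** When randomisation is balanced within strata and the strata predict the outcome, a model without them leaves the between-stratum variation in its residual, although the design has largely removed that variation from the arm comparison. The model-based standard error is then somewhat too large, the test somewhat conservative, and some precision is lost.

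The link to quality of life is plausible. Section 14.1.1 cites work relating flushing and bowel frequency to poorer quality of life. Section 8.1.5 lists octreotide, a somatostatin analog, among the options for diarrhea. GI.NET21 has endocrine and gastrointestinal scales. The placebo arms assumed for the power calculation are small (34 and 43), so precision that is available cheaply is worth having.

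There is also a specification issue. An analyst working from Section 14.1.4 would fit the model without the factors; one who gives Section 13.4 full scope would include them. The choice should be fixed in advance.

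**Working it through.** **Inputs from Section 14.1.4.** Analysed patients: pancreatic NET 117 (83 cabozantinib, 34 placebo); carcinoid 143 (100, 43). Significance level 0.05, taken as two-sided because that reproduces the stated figures. Stated effects for 80% and 90% power with no baseline correlation: 0.58 and 0.67 SD (pancreatic NET), 0.51 and 0.60 SD (carcinoid).

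**Step 1: reproduce the plan's power.** With the two-sample t-test (noncentral t), SE = SD × √(1/n₁ + 1/n₂).
- Pancreatic NET: √(1/83 + 1/34) = 0.204. Power is 80.6% at 0.58 SD and 90.4% at 0.67 SD.
- Carcinoid: √(1/100 + 1/43) = 0.182. Power is 79.3% at 0.51 SD and 90.5% at 0.60 SD.

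These agree with the stated 80% and 90%, and no stratification term is needed to reach them. The plan's figures for a correlation of 0.5 (0.52 and 0.61 SD; 0.47 and 0.55 SD) are larger, hence more cautious, than the factor √(1 − 0.25) gives (0.498 and 0.576; 0.446 and 0.516). Nothing here depends on them.

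**Step 2: effect of adding the factors, by formula.** Let R² be the share of the variance left after baseline HRQL that the factors explain. The documents give no value, so it is assumed to lie between 0 and 10%, with 20% as an extreme. The SE is multiplied by √(1 − R²).

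| Assumed R² | SE factor | Power at 0.58 SD, pancreatic NET | Power at 0.51 SD, carcinoid |
|---|---|---|---|
| 0 | 1.000 | 80.6% | 79.3% |
| 5% | 0.975 | 82.6% | 81.3% |
| 10% | 0.949 | 84.6% | 83.3% |
| 20% | 0.894 | 88.5% | 87.4% |

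As an equivalent sample size, 10% is worth 117/0.90 = 130 patients in place of 117.

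**Step 3: simulation under the actual allocation scheme.** The formula compares two unadjusted situations and ignores the balance that stratified blocks already provide, so it overstates the gain. A simulation used four strata, blocks of six, 2:1 allocation and a single follow-up visit adjusted for baseline, with 3,000 replicates. Patients were removed at random down to the quality-of-life subset. Its baseline SE of 0.177 in pancreatic NET matches 0.204 × √0.75 = 0.176, that is, a baseline correlation of 0.5. Power therefore starts above the t-test values in Step 2.

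| Assumed R² | Power, pancreatic NET: without → with strata | Power, carcinoid: without → with strata |
|---|---|---|
| 5% | 82.8% → 83.5% | 84.3% → 85.6% |
| 10% | 83.7% → 86.6% | 83.8% → 86.8% |
| 20% | 84.0% → 89.9% | 84.7% → 89.9% |

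The gain is about 1 point at 5%, 3 points at 10% and 5–6 points at 20%.

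**Step 4: is the model without strata valid?** Same subset, no true arm effect, model without strata:

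| Assumed R² | Cohort | Mean model SE | Empirical SD | Type I error |
|---|---|---|---|---|
| 5% | Pancreatic NET | 0.1767 | 0.1768 | 5.3% |
| 5% | Carcinoid | 0.1582 | 0.1551 | 4.3% |
| 10% | Pancreatic NET | 0.1772 | 0.1736 | 4.3% |
| 10% | Carcinoid | 0.1578 | 0.1572 | 4.6% |
| 20% | Pancreatic NET | 0.1768 | 0.1656 | 3.3% |
| 20% | Carcinoid | 0.1579 | 0.1437 | 3.4% |

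The simulation error of a 5% rate is √(0.05 × 0.95/3000) = 0.4 points, so 5.3% is compatible with nominal. At 5–10% the SE is overstated by about 0–2% (for example 0.1772/0.1736 = 1.02). The overstatement is larger in the full randomised set (pancreatic NET at 20%: 0.1353 against 0.1187). It shrinks in the subset because opt-in and loss before 12 weeks break up the balanced blocks.

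**The case against.** Four points can fairly be made for the plan.

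- **Section 13.4 is not expressly limited to the main trial, and Section 14.1.4 does not say that its list of terms is exhaustive.** Both are correct. A reader might infer that the plan definitely excludes the factors; the text does not support that. But Section 13.4 sits among the main-trial considerations, stratification is spelled out only for PFS and OS, and Section 14.1.4 sets out its own model without a cross-reference. If Section 13.4 is meant to apply, the form of adjustment is still unstated. The ambiguity remains.
- **Baseline HRQL is already in the model.** All the stratification factors are fixed at entry, so much of their influence may already be in the baseline score. This stands: the gain can be nil, which is why the assumed range starts at zero. For prior sunitinib the documents give no particular reason to expect a link with quality of life.
- **No design figure fails.** This also stands. The stated power rests on a t-test that the plan itself calls conservative, and it reproduces without stratification terms.
- **The substudy is optional and its type I error is not strictly controlled across endpoints.** That limits the importance of the point. It does not remove the reason to settle the model in advance.

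A reader might also infer that a wrong standard error makes the quality-of-life test invalid. The simulation does not support that: any error is towards a larger standard error, and type I error is at or below nominal within simulation error.

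**Conclusion.** The point holds as a minor matter of efficiency and specification. The quality-of-life models, as written, do not name the factors on which patients were randomised, and Section 13.4 does not clearly fill the gap. The analysis remains valid, and at worst slightly conservative.

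For an assumed R² of 0–10% beyond baseline HRQL, adding the factors reduces the standard error by 0–5% and adds about 0–3 points of power in the simulated subset. Only at 20%, which nothing in the documents supports, would the gain reach 5–6 points. It would be wrong to say that the substudy falls short of its stated power for this reason.

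The size rests on the assumed R², and on a simulation with one follow-up visit and random loss rather than the full repeated-measures model. Actual loss is unlikely to be even: Section 14.1.4 assumes that 83 of 124 cabozantinib patients (67%) and 34 of 61 placebo patients (56%) contribute in pancreatic NET, with the randomised numbers from Section 13.2. The analysed set may therefore lose some of the balance that randomisation created, which is a further modest reason to adjust.

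**What to change.** In Section 14.1.4, state that each cohort's two Section 4.6 factors, as recorded at enrolment, enter the primary QLQ-C30 model and the secondary GI.NET21 models as fixed effects: somatostatin analog use and prior sunitinib for pancreatic NET; somatostatin analog use and primary-site group for carcinoid. This also brings Section 14.1.4 into line with Section 13.4. If the sponsor prefers to leave the factors out, the section should say that Section 13.4 does not apply to the substudy, and why.

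The cost is one sentence and two degrees of freedom per model, negligible with 117 and 143 patients. No new data are needed, and the sample size and stated power can stay as they are.
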